12.8 Best Response

12.8.1 Evaluation of Best Overall Response

The best overall response is the best response recorded from the start of the treatment until disease progression/recurrence (taking as reference for progressive disease the smallest measurements recorded since the treatment started). The patient's best response assignment will depend on the achievement of both measurement and confirmation criteria.

Table 1: For Patients with Measurable Disease (i.e., Target Disease)

Target Lesions	Non-Target Lesions	New Lesions	Overall Response	Best Overall Response when Confirmation is Required*
CR	CR	No	CR	≥28 days Confirmation**
CR	Non-CR/Non-PD	No	PR	≥28 days Confirmation**
CR	Not evaluated	No	PR	
PR	Non-CR/Non-PD/not evaluated	No	PR	
SD	Non-CR/Non-PD/not evaluated	No	SD	documented at least once ≥28 days from baseline**
PD	Any	Yes or No	PD	no prior SD, PR or CR
Any	PD***	Yes or No	PD	
Any	Any	Yes	PD	

* See RECIST 1.1 manuscript for further details on what is evidence of a new lesion.
** Only for non-randomized trials with response as primary endpoint.
*** In exceptional circumstances, unequivocal progression in non-target lesions may be accepted as disease progression.

Note: Patients with a global deterioration of health status requiring discontinuation of treatment without objective evidence of disease progression at that time should be reported as “*symptomatic deterioration*.” Every effort should be made to document the objective progression even after discontinuation of treatment.

Table 2: For Patients with Non-Measurable Disease (i.e., Non-Target Disease)

Non-Target Lesions	New Lesions	Overall Response
CR	No	CR
Non-CR/non-PD	No	Non-CR/non-PD*
Not all evaluated	No	not evaluated
Unequivocal PD	Yes or No	PD
Any	Yes	PD

* ‘Non-CR/non-PD’ is preferred over ‘stable disease’ for non-target disease since SD is increasingly used as an endpoint for assessment of efficacy in some trials so to assign this category when no lesions can be measured is not advised

Table 3. Sequences of overall response assessments with corresponding best response.

1 st Assessment	2 nd Assessment	Best Response
Progression		Progressive disease
Stable, PR, CR	Progression	Progressive disease
Stable	Stable	Stable
Stable	PR, CR	Stable
Stable	Not done	Not RECIST classifiable
PR	PR	PR
PR	CR	PR
PR, CR	Not done	Not RECIST classifiable
CR	CR	CR

Table 4: Overall Response for Patients with Neuroblastoma and Measurable Disease

CT/MRI	MIBG	Bone Scan	Bone Marrow	Catechol	Overall
PD	Any	Any	Any	Any	PD
Any	PD	Any	Any	Any	PD
Any	Any	PD	Any	Any	PD
Any	Any	Any	PD	Any	PD
SD	CR/PR/SD	Non-PD	Non-PD	Any	SD
PR	CR/PR	Non-PD	Non-PD	Any	PR
CR/PR	PR	Non-PD	Non-PD	Any	PR
CR	CR	Non-PD	Non-PD	Elevated	PR
CR	CR	CR	CR	Normal	CR

Table 5: Overall Response Evaluation for Neuroblastoma Patients and MIBG Positive Disease Only

If patients are enrolled without disease measurable by CT/MRI, any new or newly identified lesion by CT/MRI that occurs during therapy would be considered progressive disease.

MIBG	CT/MRI	Bone Scan	Bone Marrow	Catechol	Overall
PD	Any	Any	Any	Any	PD
Any	New Lesion	Any	Any	Any	PD
Any	Any	PD	Any	Any	PD
Any	Any	Any	PD	Any	PD
SD	No New Lesion	Non-PD	Non-PD	Any	SD
PR	No New Lesion	Non-PD	Non-PD	Any	PR
CR	No New Lesion	Non-PD	Non-PD	Elevated	PR
CR	No New Lesion	CR	CR	Normal	CR

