12.2.1 Definitions

12.2.1.1 Evaluable for objective response: Patients who exhibit objective disease progression prior to the end of cycle 1 will be considered evaluable for response. For all other patients, only those patients who have measurable disease present at baseline, have received at least one cycle of therapy, and have had their disease re-evaluated will be considered evaluable for response.

12.2.1.2 Evaluable Non-Target Disease Response: Patients who have lesions present at baseline that are evaluable but do not meet the definitions of measurable disease, have received at least one cycle of therapy, and have had their disease re-evaluated will be considered evaluable for non-target disease. The response assessment is based on the presence, absence, or unequivocal progression of the lesions.

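### Table 3 in Section 12.8.1 gives some patients with earlier SD, PR or CR a label that the rest of the section does not support, and the plan does not settle whether confirmation applies

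*Combined protocol and SAP*

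**What the plan says.** Section 12.8.1 of the combined protocol and SAP handles best response in three places.

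- **Text.** "The best overall response is the best response recorded from the start of the treatment until disease progression/recurrence". The same paragraph adds that "best response assignment will depend on the achievement of both measurement and confirmation criteria".
- **Table 1.** Its last column applies where confirmation is required. There CR and PR need confirmation at 28 days or more, SD must be "documented at least once ≥28 days from baseline", and PD carries the condition "no prior SD, PR or CR". Footnote ** is attached to the 28-day entries and reads "Only for non-randomized trials with response as primary endpoint". The PD entry does not carry that footnote.
- **Table 3** ("Sequences of overall response assessments with corresponding best response"). Row 2 turns SD, PR or CR at the first assessment plus progression at the second into progressive disease. SD, PR or CR with no second assessment becomes "Not RECIST classifiable".

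Sections 12.2.5, 12.4.6, 12.6.2 and 12.7.7 send best response to Section 12.8. Antitumor activity is a secondary aim (1.2.1), and Section 11.5 reports response descriptively.

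Three places deal with the timing of a repeat scan: Section 12.2 (21-28 days after a response is first seen), Table 1 (at least 28 days) and Section 8.1 footnote 8 (the next consecutive cycle).

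**The concern.** Two analysts could follow the same section and label the same scans differently, one working from the text and Table 1 and the other from Table 3. The pattern is an ordinary one: disease stable at the first scan and progressing at the second. Table 3 discards the stable disease and reports progression as the patient's best result. A patient with one SD scan and no second scan drops out of the classification, although Table 1 accepts a single SD.

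Any count of stable disease or response under aim 1.2.1 therefore depends on which table is used. The choice between them would be made when the scans are already known.

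**Working it through.** No sample size, power or error rate is involved, and the plan gives no figure to reproduce. The check sets the sources side by side under each reading of confirmation.

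**Step 1: does confirmation apply?** Two places imply that it does: the 12.8.1 sentence quoted above and the confirmatory scan in Section 12.2. Footnote ** implies that it does not, because it restricts the 28-day entries to trials whose primary endpoint is response, and here response is secondary. No passage resolves this, so both readings are carried forward.

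**Step 2: compare the labels.**

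| First, then second | Table 3 | Confirmation not required | Confirmation required |
|---|---|---|---|
| SD, PD | PD | Text gives SD: conflict | SD if at least 28 days from baseline: conflict with text and Table 1. Earlier SD: no label stated |
| PR, PD | PD | Text gives PR: conflict | Table 1 literally excludes PD; the PR is unconfirmed; no label stated |
| CR, PD | PD | Text gives CR: conflict | Table 1 literally excludes PD; the CR is unconfirmed; no label stated |
| SD, not done | "Not RECIST classifiable" | SD, with the 28-day minimum lifted by footnote **: conflict | SD if at least 28 days from baseline: conflict with Table 1's SD row |

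Where confirmation is not required, the Table 1 column containing the PD condition falls away. Row 2 then conflicts with the text alone.

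**Step 3: an illustration of the SD, PD case.** A cycle is 28 days (5.1). Disease is assessed at the end of Cycle 1 and then after every other cycle (2.5, 8.1), so the second scheduled scan falls at the end of Cycle 3. That is day 3 × 28 = 84, or 84 − 1 = 83 days after day 1. Section 12.8.2 measures stable disease from the start of treatment to progression. A patient with SD at the first scan and PD at the second would therefore have about 83 days of stable disease, yet Table 3 records PD as best response. The illustration uses the standard schedule. It does not describe Part B patients under Section 8.1 footnote 14, who are evaluated every 6 months.

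**Step 4: the confirmation intervals.** The 21-28 day window in Section 12.2 and the 28-day minimum in Table 1 share only day 28 (the window ends at 28 and the minimum starts at 28). Footnote 8 in Section 8.1 gives a cycle rather than a number of days. The three are not cross-referenced.

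**The case against.** The strongest reply is that Table 3 is a confirmation table. A PR or CR followed at once by progression was never confirmed, and the text itself makes best response depend on confirmation. This stands in part. A reader might infer that row 2 contradicts both the text and Table 1 whichever way confirmation is read. The documents do not support that. Without confirmation, the Table 1 column does not apply. With it, the text does not clearly award an unconfirmed PR or CR. What remains for those sequences is a literal clash with "no prior SD, PR or CR" and a missing fallback label. The reply does not rescue row 2 for an SD that meets the minimum, because Table 1 asks for that SD only once.

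A reader might also count every Table 3 row that differs from the text when confirmation is off, such as SD then PR scored as stable. Those differences all follow from one premise, that Table 3 assumes confirmation, so they are not separate errors.

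It is tempting to say that a confirmatory scan before day 28 loses the response. The Section 12.2 scan is additional to the scheduled ones, and Table 1 sets only a minimum, so a later scheduled scan can confirm.

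Section 12.2.1.1 counts patients who "have received at least one cycle of therapy, and have had their disease re-evaluated will be considered evaluable for response", subject to measurable disease at baseline. That fixes who enters the analysis, not which label they receive. It sits awkwardly beside an unclassifiable label but does not contradict it.

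Finally, response here has no test or threshold, row 2 errs toward the worse label, and Section 8.3.2 provides central review of responders and of SD lasting 6 cycles or more. This limits the consequence. Central review supplies readings, however, and does not say how a sequence is labelled. It also would not be triggered by SD that ends at the second scheduled scan.

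**Conclusion.** The inconsistency is real and should be fixed. It is clearest for SD followed by PD, and for SD with no second assessment, wherever the SD counts: at least 28 days from baseline, or any SD if footnote ** lifts that minimum. For PR or CR followed by PD, the conflict with the text is plain only if confirmation is not required. Otherwise Table 1's wording excludes PD and nothing says what replaces it. Whether confirmation applies is itself unsettled.

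The size is limited to best-response labels for a descriptive secondary aim. MTD and RP2D, DLT, pharmacokinetic and survival results are unaffected. The documents do not show how many patients had these sequences, so no count can be given. A reader might turn the Part B cap of 6 evaluable patients (11.1) into a percentage-point shift per patient. That is not supported: it is an enrollment limit, and Section 11.2.1 defines evaluability for adverse effects, so it is not a response denominator.

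**What to change.** Before response is tabulated:

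1. Change Table 3 row 2 so that PD is best response only when there was no prior qualifying SD, PR or CR.
2. Change SD followed by no second assessment to SD when the SD meets the stated minimum.
3. State once, in light of footnote **, whether confirmation and the 28-day SD minimum apply to this trial.
4. State how a PR or CR is labelled if it is unconfirmed because the next assessment shows PD or is not done.
5. State that a later scheduled scan may confirm a response.
6. Reconcile the confirmation intervals in Section 12.2, Table 1 and Section 8.1 footnote 8.

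The cost is protocol wording, with no new scans or data. The drawback is timing. Section 2.6 records 29 patients enrolled by January 2014, so the rule would be set after many scans are known. Date and disclose the change, and show best response under both Table 3 as it stands and the corrected rule.

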8.0 EVALUATIONS/MATERIAL AND DATA TO BE ACCESSIONED

8.1 Required Clinical, Laboratory and Disease Evaluation

All clinical and laboratory studies to determine eligibility must be performed within 7 days prior to enrollment unless otherwise indicated. Laboratory values used to assess eligibility (see [Section 4.0](#)) must be no older than seven (7) days at the start of therapy. Laboratory tests need **not** be repeated if therapy starts **within** seven (7) days of obtaining labs to assess eligibility. If a post-enrollment lab value is outside the limits of eligibility, or laboratory values are older than 7 days, then the following laboratory evaluations must be re-checked within 48 hours prior to initiating therapy: CBC with differential, bilirubin, ALT (SGPT) and serum creatinine. If the recheck is outside the limits of eligibility, the patient may not receive protocol therapy and will be considered off protocol therapy. Imaging studies must be obtained within 14 days prior to start of protocol therapy (repeat the tumor imaging if necessary).

STUDIES TO BE OBTAINED	Pre-Study	During Cycle 1	During Cycles 2 & 3	Prior to Subsequent Cycles [^]	30 days, 6 months, and annually up to 60 months ^^
History	X	Weekly		X ¹⁵	X
Physical Exam with vital signs	X	Weekly		X ¹⁵	X
Blood pressure ¹	X	Weekly	Every other week (Cycle 2)	X ¹⁵	
Height, weight, BSA	X			X ¹⁵	X
Performance Status	X				
Pregnancy Test ²	X			X ¹⁵	
CBC, differential, platelets	X	Weekly ^{3,4}	Every other week	X ^{3,4,15}	
Urinalysis ⁵	X	Weekly		X ¹⁵	
Electrolytes including Ca ⁺⁺ , PO ₄ , Mg ⁺⁺	X	Weekly	Every other week	X ¹⁵	
Creatinine, ALT, bilirubin	X	Weekly	Every other week	X ¹⁵	
Albumin	X			X ¹⁵	
Amylase, lipase	X	Weekly	Every other week	X ¹⁵	
PT and INR	X				
TSH ⁶	X	Once mid-cycle (days 15-22)		X ¹⁵	
RET mutation status (germline and tumor) for patients with MTC (if available)	X				
CEA and calcitonin for patients with MTC ⁷	X	End of Cycle 1		Every other cycle x 2 then q 3 cycles	

STUDIES TO BE OBTAINED	Pre-Study	During Cycle 1	During Cycles 2 & 3	Prior to Subsequent Cycles [^]	30 days, 6 months, and annually up to 60 months ^{^^}
Tumor Disease Evaluation ^{8, 14}	X	End of Cycle 1		Every other cycle x 2 then q 3 cycles ^{8, 14}	
EKG (including QTc interval) ¹³	X	End of Cycle 1	End of Cycle 2	Every other cycle x 2 then q 3 cycles ¹³	
Plain radiograph tibial growth plate ⁹	X			X ⁹	
Patient Diary ¹⁰		Weekly		X	
Pharmacokinetics¹¹	COMPLETE	X	X	X	
Pharmacodynamics ¹²	X	X			

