⁸ Tumor Disease Evaluation should be obtained on the next consecutive cycle after initial documentation of either a PR or CR. Please note that for solid tumor patients, if the institutional investigator determines that the patient has progressed based on clinical or laboratory evidence, he/she may opt not to confirm this finding radiographically.

⁹ Plain radiographs of at least one tibial growth plate should be obtained in all patients prior to first dose of protocol therapy. In patients with open growth plates, follow-up plain radiographs of the same growth plate(s) should be obtained according to [Section 8.2.1](#).

- 10 Patient diary (see [Appendix III](#)) should be reviewed and uploaded into RAVE weekly during Cycle 1, and then after completion of each treatment cycle.
- 11 See [Section 8.4](#) and [Appendix V](#) for timing of PK studies. **COMPLETE**
- 12 See [Section 8.5](#) for timing of Pharmacodynamic/Biomarker studies and details regarding tumor tissue submission. Archival tumor tissue should be submitted for all patients. If a patient does not have tissue available, the study chair must be notified prior to enrollment.
- 13 Patients with prolonged QTc should have correctable causes of prolonged QTc addressed if possible, including medications (See [Appx. XV](#)) and correction of electrolyte abnormalities (incl. Ca^{++} and Mg^{++}). If there is no evidence of QTc prolongation after completion of 6 cycles of therapy, further EKGs are not required.
- 14 Patients currently enrolled on Part B of the study should be evaluated every 6 months.
- 15 Patients currently enrolled on Part B of the study should be evaluated/have this test performed every other cycle.

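### Section 12.8.1 conflicts with itself on best response: its text can credit a later confirmed response, but Table 3 read literally scores it Stable, and three sequences have no row

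*Combined protocol and SAP*

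**What the plan says.** Sections 12.2.5, 12.4.6, 12.6.2 and 12.7.7 send the classification of each patient to Section 12.8. Section 12.8.1 then gives two rules.

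- **Text.** "The best overall response is the best response recorded from the start of the treatment until disease progression/recurrence". It adds: "The patient's best response assignment will depend on the achievement of both measurement and confirmation criteria".
- **Table 3**, titled "Sequences of overall response assessments with corresponding best response". Its column heads are "1 st Assessment 2 nd Assessment Best Response", and no column or note covers a third assessment. The row for a response that follows stable disease reads "Stable PR, CR Stable". A first response without a second assessment falls under "PR, CR Not done Not RECIST classifiable".

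The schedule in Section 8.1 has a tumor evaluation at the end of Cycle 1, then "Every other cycle x 2 then q 3 cycles". Footnote 8 adds: "Tumor Disease Evaluation should be obtained on the next consecutive cycle after initial documentation of either a PR or CR". Section 12.2 asks for a confirmatory scan 21 to 28 days after a response is first documented. Footnote 14 puts patients currently on Part B on six-monthly evaluation.

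The double-asterisk footnote to Table 1 restricts that table's confirmation entries to non-randomized trials whose primary endpoint is response. Here antitumor activity is a secondary aim (Section 1.2.1), and Section 11.5 makes its analysis descriptive.

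**The concern.** Table 3 can return PR or CR only when the first assessment is already PR or CR. A response first seen at the second evaluation is confirmed, if at all, at a third, which the table has no column for. The confirming scan ordered by footnote 8 then cannot change the label, although the text two paragraphs above would count the patient as a responder. Such a patient could also have a duration of response under Section 12.8.2 while being tabulated as Stable.

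At stake is whether the response summary can be reproduced. Two analysts, each following Section 12.8.1, could report different response counts from the same scans. The groups are small, and the abstract singles out medullary thyroid cancer (MTC) as a focus for activity.

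**Working it through.** The plan states no figure to reproduce. The check sets the two rules side by side.

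**1. Order of assessments.** A cycle is 28 days (Section 5.1). Evaluations after Cycles 1, 3, 5 and 8 fall at about weeks 4, 12, 20 and 32. If a response first appears at week 12, the footnote 8 scan one cycle later is at about week 16 and is the third assessment. For current Part B patients footnote 14 changes the dates. The problem depends on the order of assessments, not on the weeks.

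**2. Coverage of Table 3.** Take the first assessment from {PD, SD, PR, CR} and the second from {PD, SD, PR, CR, not done}: 4 × 5 = 20 pairs. The blank second cell after a first progression is read as any result.

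- PD first: 5 pairs covered.
- SD, PR or CR, then PD: 3.
- SD, then SD, PR, CR or not done: 4.
- PR, then PR, CR or not done: 3.
- CR, then CR or not done: 2.

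The total is 5 + 3 + 4 + 3 + 2 = 17. The remaining 20 − 17 = 3 are PR-SD, CR-SD and CR-PR.

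**3. Can the three gaps occur?**

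- PR-SD: partial regrowth short of progression. In the adult phase 1 study (Section 2.3.1), 17 of 35 MTC patients had more than 30% shrinkage at least once and 10 had a confirmed PR. That leaves 17 − 10 = 7 without confirmation; the reasons are not given.
- CR-SD: a sole target node of 15 mm at baseline, then 9 mm, then 12 mm. The second value is under 10 mm (CR). The third is 3 mm above the smallest value, short of the 5 mm needed for PD, and (15 − 12)/15 = 20% below baseline, short of the 30% needed for PR.
- CR-PR: non-target lesions not evaluated at the later visit (Table 1), or markers becoming abnormal in a CNS tumor (Section 12.7.7).

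**4. Same sequence, two rules.** The text rule is read here as the best result supported by two consecutive assessments before progression.

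| Sequence | Table 3, literal | 12.8.1 text |
|---|---|---|
| SD, PR, PR | Stable | PR |
| SD, CR, CR | Stable | CR |
| SD, SD, PR, PR | Stable | PR |
| SD, PR, PR, PD | Stable | PR |
| PR, CR, CR | PR | CR |

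Enumerating every progression-free sequence that starts with SD and later contains two consecutive responses gives 4 of length three, 16 of length four and 60 of length five. Table 3 scores all of them Stable; the text scores all of them PR or CR.

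**5. Size in Part B.** Section 11.1 allows at most 6 evaluable patients. With 6 as the denominator, one relabelled patient changes the response rate by 1/6 = 16.7 percentage points.

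**The case against.** The strongest reply is that the plan, read as a whole, already counts later responses. The cross-references point to Section 12.8, not to Table 3 alone, and Section 12.8.1 opens with a rule that covers all assessments up to progression. Table 3 can be read as scoring a finding and its follow-up, so that Stable then one PR stays Stable only because the PR is not yet confirmed. Other sections fit this: a confirming scan follows any first response, responders go to central review without a time limit (Section 8.3.2), and response duration runs from whenever the criteria are met (Section 12.8.2).

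Much of this stands. A reader might infer that every response first documented at week 12 or later is lost. The documents do not support that. The loss occurs only if Table 3 is applied literally over the text, and for current Part B patients the week 4 and week 12 dates cannot be assumed. Nor can a share of affected responders be given: the documents contain no time-to-response distribution, so any percentage would come from the assumed one.

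The gaps after CR are also narrow, because recurrence ends the window and new lesions are PD. For PR-SD the text helps, since an unconfirmed PR does not meet its confirmation condition.

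The reply does not remove the conflict. Nothing says that Table 3 applies to later pairs or that the text overrides it, and the column heads name the first and second assessments.

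**Conclusion.** The concern holds as an internal contradiction. The text and Table 3 of Section 12.8.1 give different labels for a response that is first seen after a stable first assessment and then confirmed, and for PR followed by a confirmed CR. Three sequences have no label in the table.

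The consequence is limited. Response is secondary, descriptive and exploratory (Section 11.5). No sample size, DLT rule, error rate or dose decision uses Table 3, and Section 2.6 bases the recommended dose on toxicity and exposure. The figure of about 17 percentage points assumes 6 patients in the Part B response denominator and one relabelled patient. The comparison of rules assumes that confirmation applies, which the Table 1 footnote leaves unsettled. The plan should be corrected before the response tables are programmed, but nothing in the trial's conduct depends on it.

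**What to change.** In Section 12.8.1:

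1. State that the text governs where it and Table 3 differ.
2. Retitle the two assessment columns of Table 3 *any assessment* and *next assessment*, and add that best response is the best result over consecutive pairs up to progression. SD-PR-PR then yields Stable and PR, so PR; PR-CR-CR yields PR and CR, so CR. Both match the text.
3. Add rows for PR then Stable, CR then Stable, and CR then PR, with the labels the sponsor intends.
4. State whether confirmation is required in this trial, and reconcile that with the double-asterisk footnote to Table 1. The pairwise rule in item 2 builds confirmation in, so this decision comes first.

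The cost is two column heads, three rows and a few sentences. The scans are already scheduled and no new data are needed.
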